## 4 STUDY DESIGN

### 4.1 OVERALL DESIGN

The primary objective is to determine the optimal dose of CBD in children and adolescents with ASD; the hypothesis is that doseresponse curve may not be linear and that moderate doses of CBD may be therapeutically beneficial for core and associated symptoms in children and adolescents with ASD. The second objective of this study is to determine effect sizes for a variety of outcome measures, with the longer term goal of facilitating the selection of primary and secondary outcome measures for a subsequent placebo-controlled RCT. The third objective is to assess the feasibility of quantifying candidate biomarkers (e.g., resting-state functional connectivity) using MRI.

This single group single-site study will seek to enroll youth between the ages of 7 and 17 years who have a diagnosis of ASD with broadly average intelligence and who are fluently verbal. An adaptive design will be employed to allow for evaluation of optimal dosing while collecting data on core and associated ASD symptoms and any Aes that may present. Under the adaptive design algorithm we implemented, we ended recruitment after enrolling 15 participants and testing two doses. Given the higher rate of response on the higher of the two doses tested (44% vs. 16%), and the suggestion that higher doses of CBD may particularly target dopamine type 2 high affinity receptors (D2Rhigh) in the striatum, we have modified the study by implementing part 2 (described further on page 17-20), to recruit up to 15 youth (within the previously approved total accrual of 30 who would enroll) with clinical profiles that most closely resemble youth classified as responders in Part 1 of the trial.

It is important to note that all endpoints in this study are exploratory; the research base is too limited to make confident predictions. Nonetheless, given the lack of alternative pharmacological options, the benign AE profile, and the potential for CBD to fill this treatment gap, this line of work is necessary to direct future research in the field.

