### 4.2 SCIENTIFIC RATIONALE FOR STUDY DESIGN

Suggested dosing to address psychiatric symptoms may be substantially lower compared to dosing in epilepsy studies, which has been the focus of most pediatric CBD research. Further, previous research suggests that CBD has dose-dependent effects on social behavior and anxiety. Therefore, prior to conducting a double-blind trial, identifying optimal dosage is imperative. The BOIN design was employed as our dose finding approach. The BOIN design is flexible and sensitive to nonlinearity, and enables the designation of an optimal dose level based upon the proportion of participants who respond to the treatment.

The BOIN design allowed us to test the intermediate dose (n=9) and the low dose (n=6) and to observe a non-significantly higher rate of response (44%) on the intermediate dose than on the low dose (16%). Based on the overall excellent safety profile in part 1 (all participants completed treatment without any

severe adverse events or need to discontinue treatment) and the suggestion that higher doses of CBD may particularly target striatal D2Rhigh receptors, we have modified the second part of the trial to administer only the still untested 9 mg/kg/day dose, and to focus on participants who present with both ASD and ADHD, as they appear to be the ones most likely to be classified as responders in part 1. This is described in further detail on pages 17-20.

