    - Non-response: no-to-minimal therapeutic benefit captured by a CGI-I score of 3 (minimally improved) or greater (i.e., no change or any worsening) determined by consensus as indicated above, and/or severe AE, defined as severe cognitive or behavioral toxicity, impaired liver and renal function, or impaired hematopoiesis that is deemed to be potentially or likely related to study medication (also see section 8.3.2), causing early discontinuation of study intervention.

While applying a uniform statistically derived algorithm for defining treatment response and non-response for all patients would have been preferable, the above procedures were implemented given the exploratory nature of the study and the wide range of therapeutic effects that CBD may exert. The intent of this exploratory study has been to provide the foundation for a well-defined subsequent RCT.

Over the first 15 participants, we have identified five as responders, for an overall response rate of 33%, and a response rate of  $4/9 = 44\%$  on 6 mg/kg/day, as opposed to the 60% rate anticipated on the optimal dose. The response rate on 3 mg/kg/day was  $1/6 = 16\%$ . Per the BOIN design that we implemented, we have excluded both the 6 mg/kg/day and 3 mg/kg/day dose for further testing. We believe that it would be scientifically valuable to test the 9 mg/kg/day dose on the remaining 15 participants that were originally approved for this open trial. The purpose would be to further confirm the overall safety of the AE profile – which is likely given the pediatric experience with 10 mg/kg/day and 20 mg/kg/day in patients with refractory epilepsy who are more medically fragile. It has also been hypothesized that higher doses of CBD may have preferential effects on D2high receptors in the striatum. If so, that might explain why all five responders had ASD, as well as ADHD.

Accordingly, we now request that we amend the open trial to test only the dose of 9 mg/kg/day and that we require the combination of ASD and ADHD for inclusion. All other aspects of the trial would be unchanged, other than adding the Strengths and Weaknesses of Attention-Deficit/Hyperactivity Disorder Symptoms and Normal Behavior (SWAN) as a dimensional measure of ADHD and completing the K-SADS-COMP at the screening visit rather than the baseline/enrollment visit so that the study clinicians can confirm the presence of an ADHD diagnosis.

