- Computerized Kiddie Schedule for Affective Disorders and Schizophrenia (KSADS-COMP): The KSADS-COMP is a DSM-5 based instrument administered by a secure web-based computer program to parents/guardians derived from the KSADS (85). The responses and the algorithmically determined presumptive diagnoses are then immediately provided for follow-up and clarification, as needed, by a licensed clinician. The KSADS-COMP will be used in the current study to allow for further clinical characterization of the sample and will be administered to caregivers online at the enrollment/baseline visit (or at the screening visit). In Part 2 of the trial, the K-SADS-COMP will be administered at the screening visit and will also be used to confirm the presence of an ADHD diagnosis.
- Home Situations Questionnaire – Modified for ASD (HSQ-ASD): The HSQ-ASD is a 24-item questionnaire that measures behavioral noncompliance in everyday settings for children with ASD (86). The HSQ-ASD is a modified version of the HSQ (87), a measure that was initially designed for assessing noncompliance in children with disruptive behavior disorders. In its modified form, the HSQ-ASD includes an additional 7 items that address a broader range of situations in which children with ASD may display noncompliance and consists of two 12-item factors: Socially Inflexible and Demand Specific. To complete the form, caregivers indicate whether the child has a problem with compliance in each situation and, if so, to rate the severity of non-compliance on a 1–9 Likert scale. Higher scores indicate greater non-compliance. The HSQ-ASD will be completed by caregivers at the enrollment/baseline visit (or at the screening visit) and the final study visit (Week 6), and 6 weeks after medication discontinuation (optional), and takes approximately 10 minutes to complete.

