#### 9.4.7 SUB-GROUP ANALYSES

Not applicable.

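### Part 2 is limited to children with ASD and ADHD because all five Part 1 responders had ADHD, but no ADHD count is reported for the ten non-responders

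*Combined protocol and SAP*

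**What the plan says.** Section 6.1.2 reports the Part 1 result: "Over the first 15 participants, we have identified five as responders, for an overall response rate of 33" per cent. Four of the nine children on 6 mg/kg/day responded, and one of the six on 3 mg/kg/day. The same section cites a hypothesis that higher doses act preferentially on high-affinity D2 receptors in the striatum, and adds "that might explain why all five responders had ASD, as well as ADHD". It then makes ADHD a requirement for Part 2, and section 5.1 lists this as an inclusion criterion confirmed by K-SADS-COMP.

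Section 4.2 gives the reason for choosing children with both diagnoses, saying that Part 2 will "focus on participants who present with both ASD and ADHD, as they appear to be the ones most likely to be classified as responders in" the earlier stage (Part 1). Section 4.1 describes the Part 2 population as youth with "clinical profiles that most closely resemble youth classified as responders in Part 1 of the trial".

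In section 8.1 the K-SADS-COMP is to be "used in the current study to allow for further clinical characterization of the sample", given at baseline or screening. Section 6.1.2 moves it to screening for Part 2. Section 9.4.7, on subgroup analyses, reads "Not applicable".

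**The concern.** The statement in section 4.2 is about the probability of response given ADHD. The figure behind it is the frequency of ADHD given response. To get from one to the other, the reader needs the ADHD count among the ten non-responders. The documents do not report that count, the ADHD prevalence in the 15, response rates with and without ADHD, or any test or interval. If ADHD was common in the Part 1 sample, five out of five is unremarkable. If it was uncommon, five out of five is striking.

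Two things are at stake. First, the responder profile decides who enters Part 2, and Part 2 contains no child without ADHD against whom the profile could be checked. Second, sections 9.4.1 and 9.4.2 choose the optimal dose by comparing response rates across doses, and section 6.1.2 would read a low Part 2 rate as evidence for 6 mg/kg/day. The 9 mg/kg/day rate will come only from children with ADHD. The two earlier rates come from children not selected for it. Dose and selection are therefore mixed in that comparison.

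**Working it through.** **Inputs.** From sections 4.2 and 6.1.2: 15 Part 1 children, 5 responders (4 of 9 on 6 mg/kg/day, 1 of 6 on 3 mg/kg/day), 10 non-responders, and ADHD in 5 of 5 responders. Not given: m, the number of the 15 with ADHD. It must lie between 5 and 15, so the whole range is shown.

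**The plan's own figures.** 5/15 = 33.3%, 4/9 = 44.4% and 1/6 = 16.7%. These agree with the printed 33%, 44% and 16%, the last being truncated.

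**Chance of five out of five with no association.** If response is unrelated to ADHD, the five responders are a random five of the 15, so

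P = C(m,5) / C(15,5), with C(15,5) = 3003.

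For example, m = 9 gives 126/3003 = 4.2% and m = 12 gives 792/3003 = 26.4%. The Fisher p values are two-sided and compare 5/5 responders with (m − 5)/10 non-responders. No responder lacked ADHD, so the response rate is 5/m with ADHD and 0/(15 − m) without.

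| m of 15 with ADHD | Non-responders with ADHD | P(all 5 responders have ADHD, no association) | Fisher p | Response with ADHD | Response without ADHD |
|---|---|---|---|---|---|
| 5 | 0/10 | 0.03% | 0.0003 | 5/5 = 100% | 0/10 |
| 7 | 2/10 | 0.7% | 0.007 | 5/7 = 71% | 0/8 |
| 8 | 3/10 | 1.9% | 0.026 | 5/8 = 62.5% | 0/7 |
| 9 | 4/10 | 4.2% | 0.044 | 5/9 = 56% | 0/6 |
| 10 | 5/10 | 8.4% | 0.10 | 5/10 = 50% | 0/5 |
| 11 | 6/10 | 15% | 0.23 | 5/11 = 45% | 0/4 |
| 12 | 7/10 | 26% | 0.51 | 5/12 = 42% | 0/3 |
| 13 | 8/10 | 43% | 0.52 | 5/13 = 38% | 0/2 |
| 14 | 9/10 | 67% | 1.0 | 5/14 = 36% | 0/1 |
| 15 | 10/10 | 100% | 1.0 | 5/15 = 33% | no such children |

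The chance is below 5% for m up to 9, and above 25% only for m of 12 or more.

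**The planning rate.** Section 6.1.2 expects at least one third of Part 2 children to respond. That equals the unselected 5/15. The Part 1 rate among children with ADHD, 5/m, equals one third only if all 15 had ADHD, and otherwise exceeds it. The wording is a lower bound, so this is no contradiction, but the planning figure gives no sign of enrichment.

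**The like-for-like comparator.** At each Part 1 dose there were five non-responders, of whom anywhere from none to five may have had ADHD. The ADHD-only rate at 6 mg/kg/day therefore lies between 4/9 = 44% and 4/4 = 100%. At 3 mg/kg/day it lies between 1/6 = 17% and 1/1 = 100%. In both cases the published all-comer rate is the lowest value that the ADHD-only rate can take.

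**The case against.** The strongest reply is that the documents do not rest on the five responders alone. They give a mechanistic reason and link it to ADHD. Their language is hedged, and section 4.1 calls every endpoint exploratory. The K-SADS-COMP was planned for the whole sample, so the investigators may have made the comparison without reporting it. Sections 9.4.5 and 9.4.8 promise baseline summaries and individual listings from which the table might be built.

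Much of this stands, and it limits the point to a missing reported comparison. It does not supply one. No responder data are shown for the receptor hypothesis, and it concerns higher doses, whereas the five responders took the two lower ones. Calling the endpoints exploratory excuses imprecision but does not replace the comparison group. The listings might allow the table, but no section commits to it.

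A reader might infer more than the documents support:

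- *That this kind of selection would often pick out ADHD by chance.* That depends on m, which is unknown. For m from 5 to 9 the chance is below 5%.
- *That some shared trait was bound to emerge from so large a battery.* No search across traits is described, and any figure would depend on an assumed number of traits and their prevalence.
- *That the trial will report ADHD as a responder marker or fix the later trial's population by it.* No section says so. What the documents carry forward is a dose and a choice of outcome measures.

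**Conclusion.** The point holds as a gap in reporting and comparison. The claim in section 4.2 about who responds has no reported comparative support, and Part 2 as designed can neither test it nor separate it from the dose effect. The size of the problem cannot be fixed from the documents: the chance of five out of five with no association runs from 0.03% to 100%, and Fisher's p from 0.0003 to 1.0, according to m. The documents therefore do not show that the ADHD profile is a chance finding, any more than they show that it is real.

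The calculation assumes that the reported counts are correct and that, with no association, any five of the 15 children were equally likely to be the responders. It ignores the difference in dose. The remedy assumes that K-SADS-COMP was completed in Part 1 as planned, which the documents imply but do not confirm child by child.

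**What to change.** 1. In section 9.4.7, replace the present entry with Part 1 response by baseline K-SADS-COMP ADHD status, overall and by dose. Give responders over total with and without ADHD, exact 95% confidence intervals, and an exact interval for the overall difference. Label it descriptive, given 15 children. Attach no significance rule: a non-significant difference at this size would not show that ADHD is irrelevant.
2. In section 9.4.2, state that when doses are compared, the ADHD-only Part 1 rates will be shown beside the Part 2 rate.
3. In sections 4.2 and 6.1.2, replace the claim about who is likeliest to respond, and the inference from the five responders, with the two observed rates. State that the ADHD criterion was chosen after Part 1 results were seen, is hypothesis-generating, and can be neither tested in Part 2 nor separated there from the effect of dose.

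Eligibility need not change. The cost is one table from data already planned and a few reworded sentences. The stated rationale may look weaker, the by-dose intervals will be very wide (nine and six children, split further by ADHD), and the ADHD-only Part 1 rates may be optimistic because the trait was chosen by looking at the responders.

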#### 4.3 JUSTIFICATION FOR DOSE

Chronic CBD dosing up to 1500 mg/day has been reported to be tolerated well without AE (60-63); minor AE were reported after CBD use in children with epilepsy being treated with multiple other medications in doses up to 50 mg/kg/day (3, 27). Accordingly, we believe an upper limit of 9 mg/kg/day orally in our dose finding approach is reasonable and safe. Our proposed dosage range is substantially lower than most pediatric studies registered in ClinicalTrials.gov (accessed on 06 February 2018). Our dose range (3-9 mg/kg/day) is comparable to the only ongoing study specifically addressing behavioral symptoms in ASD (NCT02956226; dose range 1 mg/kg/day to 10 mg/kg/day). As mentioned, participants assigned to the highest dose (9 mg/kg/day) will be instructed to take half the dose (4.5 mg/kg/day, divided in two doses) per day for the first week of treatment before increasing to the full dose to minimize the chance for adverse events upon treatment initiation. This will go into effect when the next cohort of participants begin treatment with CBD; therefore, all participants who have already been enrolled will not be re-consented or informed of the changes.

The BOIN design, discussed in detail within the Dosing and Administration section of the protocol, was informed by the observation of dose-dependent inverted-U effects on social behavior in a mouse model of Dravet syndrome in which social effects were observed at lower doses than anti-seizure effects (2), the increased efficacy of CBD in reducing anxiety during a public speaking task at a moderate dose compared to a low and high dose (9), and correspondence with [name] regarding his clinical experiences in prescribing CBD to address associated symptoms of ASD. As noted, now that we've obtained data from 15 participants on the low and intermediate doses by implementing the BOIN design, we propose to test the remaining 9 mg/kg/day dose in up to 15 participants – within the originally approved accrual ceiling of 30.

#### 4.4 END OF STUDY DEFINITION

A participant is considered to have completed the study if he or she has completed all phases of the study including the last in-person visit (Visit 4 shown in the SOA, Section 1.3).

### 5 STUDY POPULATION

#### 5.1 INCLUSION CRITERIA

Patients who will be selected for this study will meet the following criteria:

- Male or female pediatric outpatients aged between and including 7 to 17.9 years old
- Diagnosis of ASD confirmed by the ADOS-2 or CARS-2-HF and DSM-5 criteria

- Part 2: Diagnosis of ADHD confirmed by clinician review of the K-SADS-COMP
- SRS-2 Total T-score of 66 or higher
- CGI-S score of 4 or higher
- Physical exam and laboratory results that are within normal range for their age
- Fluent speech
- Estimated IQ of at least 80
- Presence of a parent/legal guardian who is able to consent for their participation and complete assessments regarding the child's development and behavior throughout the study
  - Child Assent will be obtained.

## 5.2 EXCLUSION CRITERIA

Patients cannot be included in the study if:

- History of active seizure disorder or epilepsy; patients seizure free for > 5 years off of antiepileptic drugs and other than uncomplicated febrile seizures are not excluded
- History or current evidence of significantly impaired liver function, defined as 1) Alanine aminotransferase (ALT) and/or aspartate aminotransferase (AST) > 5 × upper limit of normal (ULN); 2) ALT or AST > 3 × ULN with concomitant total bilirubin > 2.0 × ULN; or 3) ALT or AST ≥ 3 × ULN with the appearance of fatigue, nausea, vomiting, right upper quadrant pain or tenderness, fever, rash, and/or eosinophilia.
- Exposure to any investigational agent in the 30 days prior to initiation of trial
- Treatment with CBD or other cannabinoid within the previous two months
- Current use of medications metabolized primarily by CYP2B6, CYP2C8, CYP2C9, CYP2C19, CYP3A4, or CYP2D6 isoenzymes. Methylphenidate is not contraindicated as it is rapidly and extensively metabolized by carboxylesterase CES1A1 to ritalinic acid, which has little to no pharmacologic activity per DrugBank (accessed 1/31/19: [www.DrugBank.ca/drugs/D800422](http://www.DrugBank.ca/drugs/D800422)).
- History of drug abuse including marijuana/cannabis use in the past 3 months
- Positive urine sample results from drug screening indicating presence of the following drugs: THC, opiates, methamphetamine, or cocaine
- Diagnosis of a known genetic disorder (e.g., Prader-Willi Syndrome, Angelman Syndrome, etc.).
- Active suicidality (ideation and plan) is present
- A current psychiatric diagnosis of bipolar disorder, major depressive disorder (MDD), psychosis, schizophrenia, or post-traumatic stress disorder (PTSD)
  - These patients will be excluded due to potential confounding results.
- Pregnant or lactating patients or patients who will not agree to be abstinent or use contraception
  - CBD has not been studied in pregnant or lactating females.
- A medical condition that severely impacts the subject's ability to participate in the study, interferes with the conduct of the study, confounds interpretation of study results or endangers the subject's well-being
- Diagnosis of Rett Syndrome or Childhood Disintegrative Disorder or marked sensory impairment such as deafness or blindness
- Subjects who have had changes in allied health therapies, behavioral or educational interventions within 4 weeks prior to initiation of trial, other than those associated with school holidays
- Subjects who have had changes in non-exclusionary psychotropic medications within 4 weeks of initiation of trial

### *Lifestyle Considerations*

During this study, participants are asked to:

- Refrain from making changes in allied health therapies, behavioral or educational interventions
- Refrain from making changes in non-exclusionary psychotropic medication (e.g., methylphenidate) regimen or dosage
- Abstain from illicit drugs, particularly THC, opiates, methamphetamine and cocaine
- Use abstinence or use a valid method of contraception

If prohibited medication, treatment, or practices are indicated during the trial, the participant will be withdrawn from the trial. Notably, if the patient/caregiver states they plan to discontinue exclusionary medications to participate in the trial, they will be required to do so under the care of their treating physician, and will remain under that clinician's care during the titration/discontinuation and throughout their participation in this study.

Importantly, participants will be screened for contraindications to MRI scanning (e.g., metal implants, pacemakers, metal foreign bodies, pregnancy). They will not be permitted to undergo optional scanning if they meet a condition that is contraindicated.

## 5.3 SCREEN FAILURES

Screen failures are defined as participants who consent to participate in the clinical trial but do not enter the study. A minimal set of screen failure information is required to ensure transparent reporting of screen failure participants, to meet the Consolidated Standards of Reporting Trials (CONSORT) publishing requirements and to respond to queries from regulatory authorities. Minimal information includes demography, screen failure details, eligibility criteria, and any SAE.

Individuals who do not meet the criteria for participation in this trial (screen failure) because of a modifiable factor (e.g., changed treatment regimen 3 weeks prior to screening) may be rescreened. Rescreened participants should be assigned the same participant number as for the initial screening.

